#### **6.10 Follow-up Phase**

Patients will be followed every 12 weeks for two years after completion of the study or until death, whichever occurs first. Patients that have been removed from the study for serious or adverse events will be followed until resolution or stabilization of the event.

#### **6.11 Study Intervention/Follow-up Compliance**

Patients will be monitored closely by the research staff for protocol compliance, including follow up visits and imaging. Pills in the pill bottle will be returned by the patients and pills counted to assure compliance.

#### **6.12 Lost to Follow Up**

The following actions must be taken if a participant fails to return to the clinic for a required study visit:

- The site will attempt to contact the participant and reschedule the missed visit within 2 weeks and counsel the participant on the importance of maintaining the assigned visit schedule and ascertain if the participant wishes to and/or should continue in the study.
- Before a participant is deemed lost to follow-up, the investigator or designee will make every effort to regain contact with the participant (where possible, 3 telephone calls and, if necessary, a certified letter to the participant's last known mailing address or local equivalent methods). These contact attempts should be documented in the participant's medical record or study file.
- Should the participant continue to be unreachable, he or she will be considered to have withdrawn from the study with a primary reason of lost to follow-up.]

## **7 STUDY INTERVENTION**

### **7.1 Study Intervention/Device Description**

During the treatment phase, subjects will receive cabozantinib until either disease progression, the occurrence of drug-related toxicity, or for other reason(s) for subject withdrawal described in Section 7.9. Subjects will be instructed to immediately inform the principal investigator (PI) of any AEs.

Treatment will be administered on an outpatient basis. Reported adverse events and potential risks are described in Section 7. Subjects experiencing dizziness, sleepiness, or other symptoms that could influence alertness or coordination should be advised not to drive or operate other heavy machinery. If required, appropriate dose modifications for cabozantinib are described in Section 7.7.1.

### **7.2 Potential Drug Interactions**

Cabozantinib is a CYP3A4 substrate and a weak substrate for CYP2C9 (but not a CYP2D6, CYP2C8, CYP2C19, CYP2B6, or CYP1A2 substrate). Co-administration of cabozantinib with strong inducers of the CYP3A4 family (e.g. dexamethasone, phenytoin, carbamazepine, rifampin, rifabutin, rifapentin, phenobarbital, and St. John's Wort) may significantly decrease cabozantinib concentrations. The chronic use of strong CYP3A4 inducers after treatment should be avoided. Other drugs that induce CYP3A4 should be used with caution because these drugs have the potential to decrease exposure (AUC) to cabozantinib. Selection of alternate concomitant medications with no or minimal CYP3A4 enzyme induction potential is recommended.

Caution must be used when discontinuing treatment with a strong CYP3A4 inducer in a subject who has been concurrently receiving a stable dose of cabozantinib, as this could significantly increase the exposure to cabozantinib.

Reduce the dosage of cabozantinib if concomitant use with strong CYP3A4 inhibitors cannot be avoided as detailed in the package insert.

### 7.3 Availability

Cabozantinib is an investigational agent that will be supplied by Exelixis.

### 7.4 Acquisition and Accountability

Agent Inventory Records/Device Logs – The investigator, or a responsible party designated by the investigator, will maintain a careful record of the inventory and disposition of all agents/device received from Sponsor on a Drug Accountability Record Form (DARF) or Device Log.

The investigator or designee will maintain accurate records of receipt of all study treatment including dates of receipt. In addition, accurate records will be kept regarding the date, lot number, and how much study treatment is dispensed and used by each subject in the study. Reasons for deviation from the expected dispensing regimen must also be recorded. At completion of the study, to satisfy regulatory requirements regarding drug accountability, all unused study treatment will be reconciled and destroyed according to applicable state, federal, and local regulations.

### 7.5 Formulation, Appearance, Packaging, and Labeling

At study sites, all study medication will be stored as described in the appropriate prescribing information for that country (if applicable) or the pharmacy manual and inventoried in accordance with applicable state and federal regulations.

Cabozantinib tablets are supplied as film coated tablets containing cabozantinib malate equivalent to 20mg of cabozantinib and contain microcrystalline cellulose, lactose anhydrous, hydroxypropyl cellulose, croscarmellose sodium, colloidal silicon dioxide, magnesium stearate and Opadry® yellow. Doses of 40 mg will comprise two 20-mg tablets. The components of the tablets are listed in Table 7.1.

**Table 7.1: Cabozantinib Tablet Components and Composition**

Ingredient	Function	% w/w a
Cabozantinib Drug Substance (25% drug load as free base)	Active Ingredient	31.68

Microcrystalline Cellulose (Avicel® PH-102)	Filler	38.85
Lactose Anhydrous (60M)	Filler	19.42
Hydroxypropyl Cellulose (EXF)	Binder	3.00
Croscarmellose Sodium (Ac-Di-Sol®)	Disintegrant	6.00
Colloidal Silicon Dioxide	Glidant	0.30
Magnesium Stearate	Lubricant	0.75
Opadry® yellow film coating which includes HPMC 2910/hypromellose 6 cp, titanium dioxide, triacetin, and iron oxide yellow	Film Coating	4.00

a weight fraction, expressed in percentage; HPMC, hydroxypropyl methylcellulose

## 7.6 Product Storage and Stability

Refer to the Investigator's Brochure for details on storage and handling of cabozantinib.

## 7.7 Preparation

Cabozantinib is supplied as a capsule formulation with dose strengths of 20 mg. The capsules are two-piece hard gelatin capsules with "XL184 20 mg" printed on the body of the capsule shell. No preparation is necessary.

## 7.8 Dosing and Administration

Subjects will receive cabozantinib orally at a (starting) dose of 40 mg once daily.

Cabozantinib must be taken on an empty stomach. Subjects must be instructed not to eat for at least 2 hours before and at least 1 hour after taking cabozantinib. Subjects should be instructed to take their cabozantinib dose at approximately the same time every day. If a subject misses a dose, the dose may be taken later only if it is within 12 hours of when the missed dose should have been taken. The missed dose should not be made up if it is within 12 hours of the next scheduled dose.

Cabozantinib tablets should be swallowed whole with at least 8 ounces of water. The tablets should not be crushed. Grapefruit, grapefruit juice, Seville oranges and their products should be avoided by subjects taking cabozantinib.

### 7.8.1 Dosing Delays/Dose Modifications

The following should be taken into consideration in decisions regarding dose modifications (reductions or interruption):

- As a general approach all AEs should be managed with supportive care at the earliest signs of toxicity considered related to the study treatment. Should this be ineffective, dose interruptions and/or reductions should be considered to prevent worsening of toxicity.
- The assigned starting dose for cabozantinib is 40 mg/day. Two dose reduction levels of cabozantinib is permitted (see Table 7.2).
- Dose modification criteria for cabozantinib are shown in Table 7.2. Dose interruptions and/or reductions should be implemented for unacceptable toxicity. Doses may be

modified at any time while a subject is on treatment.

- Dose reductions or interruptions may also occur in the setting of lower grade toxicity than defined in Table, if the investigator feels it is in the interest of a subject's safety and will optimize drug tolerability.
- Interruption of cabozantinib treatment for cabozantinib-related AEs may occur at any time per investigator discretion. If treatment is interrupted due to related AEs for more than 6 weeks, cabozantinib should be discontinued unless there is unequivocal evidence that the subject is benefitting. In this situation, a subject may be able to restart therapy with a dose reduction upon resolution of the toxicity per the discretion of the investigator.
- Dose interruptions for reason(s) other than related AEs (e.g., surgical procedures) can be longer than 6 weeks per the discretion of the investigator.

General management of cabozantinib dosing related to AEs is in Section 7.8.1 and additional guidelines for the management of specific AEs are provided in Section 7.9

**Table 7.2: Dose Reductions of cabozantinib**

Assigned Dose	First Dose Level Reduction	Second Dose Level Reduction
40-mg cabozantinib oral qd	20-mg cabozantinib oral qd	20-mg cabozantinib oral every other day
20-mg cabozantinib oral qd	20-mg cabozantinib oral every other day	No dose reduction permitted

**NOTE:** cabozantinib will be discontinued if a every other day (eod) dose of 20 mg cabozantinib(minimum dose) is not tolerated.

**Table 7.3: Dose Modifications of Cabozantinib for Treatment-Related AEs**

Event	Management
Grade 1 AEs	Add supportive care as indicated. Continue cabozantinib treatment at the current dose level if AE is manageable and tolerable.
Grade 2 AEs which are tolerable and are easily managed	Continue cabozantinib treatment at the current dose level with supportive care.
Grade 2 AEs which are intolerable and cannot be adequately managed	At the discretion of the Investigator, cabozantinib should be dose reduced or interrupted.  Note: It is recommended that dose holds be as brief as possible.

Grade 3 AEs (except clinically non-relevant laboratory abnormalities)	Cabozantinib should be interrupted unless the toxicity can be easily managed with a dose reduction and optimal medical care.  Note: It is recommended that dose holds be as brief as possible.
Grade 4 AEs (except clinically non-relevant laboratory abnormalities)	Subjects should have cabozantinib interrupted immediately. Discontinue cabozantinib unless the following criteria are met: 
 
• Subject is deriving clear clinical benefit as determined by the Investigator, and approved by the Principal Investigator.
 
• Toxicity can be managed with a dose reduction following recovery to Grade 1 (or baseline) and optimal medical care .
 

Note: The dose delay and modification criteria for specific medical conditions are provided in Section 7.7.1	

### **7.8.2 Cabozantinib Dose Reinstitution and Reescalation**

If the subject recovers from his or her toxicities to CTCAE v.4.0 Grade  $\leq 1$  or to the baseline value (or lower) and the toxicity was unrelated to study treatment, then study treatment may be restarted with no change in dose.

If the subject recovers from his or her toxicities to Grade  $\leq 1$  or to the baseline value (or lower) the toxicity was deemed possibly related to study treatment, then study treatment may be restarted at a reduced dose (see Table 7.2 for the schedule of dose reductions).

Subjects receiving a daily dose of 20 mg may be restarted at the same dose if deemed safe at the discretion of the investigator. Subjects unable to tolerate a daily dose of 20 mg should discontinue study treatment.

Re-escalation to the previous dose, (but not higher than 40 mg/day) may be allowed at the discretion of the investigator for AEs which have resolved or recovered to Grade 1 (or baseline value) and deemed tolerable and easily managed by optimized supportive treatment. Dose re escalation is not allowed for a drug-related dose reduction triggered by Grade 4 hematologic toxicities or by Grade 4 AEs affecting major organs (e.g. central nervous system, cardiac, hepatic, renal).

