## 1. PROTOCOL SUMMARY

Full Title	Open Label Phase II Trial of Cabozantinib in Patients with Metastatic Castrate Resistant Prostate Cancer (mCRPC) and Known Amplifications or Activating Mutations in Gene Targets of Cabozantinib or Liver Metastases who have Received Prior Anti-Androgen Therapy
Short Title	Cabozantinib for mCRPC
Clinical Phase	Phase 2
Principal Investigator	[name]
Sample Size	N = 30
Accrual Ceiling	Enroll up to 30 subjects and screen up to 100 subjects
Study Population	Men with CRPC who have progressed on a second-line anti-androgen therapy
Accrual Period	24 months
Study Design	
This is a phase II non-randomized, open label trial designed to evaluate treatment response and survival of patients with mCRPC who harbor evidence of increased signaling (via evidence of DNA amplification or RNA overexpression) of the targets of cabozantinib (MET, KIT, RET, VEGFR-1 (FLT1), VEGFR-2 (KDR), VEGFR-3 (FLT4), FLT3, AXL, TRKB, and TIE2) or who have or liver metastases.
 
All patients will receive cabozantinib at 40 mg/day. Dose reduction (from 40 to 20 mg and to 20 mg every other day) or interruptions of treatment will be allowed for unacceptable adverse events (AEs).

Study Duration	Approximately 12 months after enrollment, then patients will shift to long-term follow up
Study Agent	Cabozantinib, 40 mg PO daily
Primary Objective	To assess the radiographic response proportion of cabozantinib in patients with metastatic CRPC who have progressed on an androgen receptor signalinginhibitor whose tumor possess a molecular abnormality that is targeted by cabozantinib or who have liver metastases
Secondary Objectives	
 
• To assess PSA decline by PCWG3
 
• To measure overall survival (OS)
 

Exploratory Objectives	
 
• To explore prognostic and/or predictive biomarkers of cabozantinib in whole blood, plasma and tumor samples: 
 
○ To evaluate for and measure changes in targeted genes found in cell-free DNA at baseline, in response to treatment, and at the time of disease progression
 
○ To explore the effects of cabozantinib on
 
 
 

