**Table 7.6: Management of Hand-Foot Syndrome (PPES) Associated with Cabozantinib**

Event	Management
Grade 1	Cabozantinib treatment may be continued at the current dose if PPES is clinically insignificant and tolerable. Otherwise, cabozantinib should be reduced to the next lower dose level. a Start urea 20% cream twice daily AND clobetasol 0.05% cream once daily. Reassess at least weekly; if PPE worsens at any time or does not improve after 2 weeks, proceed to the intervention guidelines for Grade 2.
Grade 2	Cabozantinib treatment may be continued if PPES is tolerated. Cabozantinib should be dose reduced or interrupted if PPES is intolerable. Continue urea 20% cream twice daily AND high potency steroid cream (e.g., clobetasol 0.05%) once daily and add analgesics (e.g., NSAIDs/gamma-aminobutyric acid agonists) for pain control if needed. Reassess at least weekly; if PPE worsens or affects self-care, proceed to the intervention guidelines for Grade 3.
Grade 3	Interrupt cabozantinib treatment until severity decreases to Grade 1 or 0. Continue treatment of skin reaction with high potency steroid cream (e.g., clobetasol 0.05%) twice daily AND analgesics. Resume cabozantinib at a reduced dose if PPES recovers to Grade ≤ 1. Discontinue subject from cabozantinib if PPES does not improve within 6 weeks.
b Permitted dose levels are defined by individual protocols.	

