### **7.10 Duration of Therapy and Criteria for Removal from Study**

Subjects may discontinue study treatment or withdraw their consent to participate in the study at any time without prejudice. The investigator may withdraw a subject from study treatment or from the study if, in his or her clinical judgment, it is in the best interest of the subject or if the subject cannot comply with the protocol.

In addition, any of the following conditions require discontinuation of the subject from study treatment:

- An AE or intercurrent illness that in the opinion of the investigator warrants the subject's withdrawal from study treatment;
- The investigator believes it is not in the best interest of the subject to continue on study
- Specific conditions described in the Management of Adverse Events Section;
- Necessity for treatment with other anticancer treatment prohibited by protocol;
- Sexually active subjects who refuse to use medically accepted barrier methods of contraception (e.g., male condom, female condom) during the course of the study and for 4 months after discontinuation of study treatment;

- If the subject does not recover from his or her toxicities to tolerable Grade  $\leq 2$  within 6 weeks, the subject will have study treatment discontinued unless there is unequivocal evidence that the subject is benefitting. In this situation, a subject may be able to restart therapy with a dose reduction upon resolution of the toxicity and with agreement of the principal investigator / Sponsor;
- Request by regulatory agencies for termination of treatment of an individual subject or all subjects under the protocol;
- Significant noncompliance with the protocol schedule in the opinion of the investigator;
- Subjects who cannot tolerate the minimum protocol-specified dose of study treatment will have study treatment discontinued;
- Progressive disease (PD) or the subject no longer experiences clinical benefit as determined by the investigator

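### Section 7.8.2 stops patients who cannot tolerate 20 mg daily, one level above the minimum dose set in Table 7.2 (minor; wrong as written)

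*Combined protocol and SAP*

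**What the plan says.** The dose-reduction rules appear in five places in the combined protocol and SAP.

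- **Section 1, Protocol Summary (Study Design):** "Dose reduction (from 40 to 20 mg and to 20 mg every other day".
- **Section 7.8.1:** the starting dose is 40 mg/day, and "Two dose reduction levels of cabozantinib is permitted (see Table 7.2".
- **Table 7.2:** the level below 20 mg daily is "20-mg cabozantinib oral every other day". It is the second reduction for a patient who started at 40 mg and the first for a patient on 20 mg daily. The NOTE adds: "cabozantinib will be discontinued if a every other day (eod) dose of 20 mg cabozantinib(minimum dose) is not tolerated".
- **Section 7.8.2:** after recovery from toxicity that is possibly related, "study treatment may be restarted at a reduced dose (see Table 7.2 for the schedule of dose reductions". The next paragraph lets patients on 20 mg daily restart at the same dose if the investigator considers it safe, and then says: "Subjects unable to tolerate a daily dose of 20 mg should discontinue study treatment".
- **Section 7.10:** "Subjects who cannot tolerate the minimum protocol-specified dose of study treatment will have study treatment discontinued".

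**The concern.** For a patient who fails 20 mg daily, the protocol gives two different instructions. Table 7.2 offers him one more level and makes failure at that level the trigger for stopping. The last sentence of that paragraph in 7.8.2 stops him at once. No passage says which instruction prevails.

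This is an operative rule for ending treatment. A site that works from 7.8.2 would take off drug a patient whom the dose ladder allows to continue, while a site that works from Table 7.2 would keep him on. Section 4.7 expects about eight sites, so the same toxicity could be handled differently across the trial, and following either instruction departs from the other.

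**Working it through.** The plan states no figure on this point to reproduce. The check sets the rules side by side and counts levels.

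**Inputs.** Starting dose of 40 mg daily and two permitted reductions (7.8.1); the ladder (synopsis and Table 7.2); the named minimum dose (Table 7.2 NOTE); the stopping sentence (7.8.2); the general stopping criterion (7.10).

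**Step 1: count the levels.**

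| Source | Dose levels | Reductions | Stop when this dose is not tolerated |
|---|---|---|---|
| Synopsis, 7.8.1, Table 7.2 and NOTE | 40 mg daily, 20 mg daily, 20 mg every other day (3) | 3 − 1 = 2 | 20 mg every other day |
| 7.8.2, stopping sentence | 40 mg daily, 20 mg daily (2) | 2 − 1 = 1 | 20 mg daily |

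The difference is 2 − 1 = 1 reduction, so the 7.8.2 sentence stops treatment exactly one level before the stated minimum.

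**Step 2: can the 7.8.2 phrase cover every-other-day dosing?** No. Table 7.2 lists once-daily and every-other-day 20 mg as separate levels, and the latter averages 20 / 2 = 10 mg per day.

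**Step 3: does the sentence govern restarts only?** The title of 7.8.2 concerns reinstitution and re-escalation, so this reading is possible, but it does not remove the conflict. The preceding paragraph of the same section sends restarts after related toxicity to Table 7.2. For a patient on 20 mg daily, the only lower level there is 20 mg every other day. Section 7.8.2 is therefore at odds with itself on restarts, and Table 7.2 makes no exception for them.

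**Step 4: which text is the outlier?** The synopsis, 7.8.1, Table 7.2 and its NOTE agree. Section 7.10 ties stopping to the minimum dose without naming it, and the NOTE is where a minimum dose is named. The single 7.8.2 sentence stands alone.

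**Step 5: is any statistical quantity affected?** No sample size, confidence interval or other stated figure in section 12 depends on the number of dose levels.

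**The case against.** The strongest reply is that the intended rule is easy to identify. Four places agree on the every-other-day floor, 7.10 is compatible with them, and the Table 7.2 NOTE is phrased as a requirement while the 7.8.2 sentence is phrased as advice. The preceding sentence of 7.8.2, on restarting at the same 20 mg daily dose, is permissive and conflicts with nothing. On this view the point is an editorial slip. That argument stands as to severity. It does not remove the contradiction, because advice to stop is still the opposite of the step that the table offers.

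Three stronger readings are tempting, and the documents do not support them.

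- **That the adverse-event tables contradict 7.8.2 outright.** Some direct a step down; Table 7.6, for example, says of Grade 1 hand-foot syndrome that is not both insignificant and tolerable: "Otherwise, cabozantinib should be reduced to the next lower dose level". But the 7.8.2 sentence applies only to a patient judged unable to tolerate 20 mg daily. Tables 7.7 and 7.8 act on laboratory thresholds, which do not by themselves amount to that judgment. Any conflict there is conditional. The direct conflict is with the synopsis, 7.8.1 and Table 7.2.
- **That the sentence costs the trial evaluable patients.** Section 12.5.2 assesses response after at least 3 cycles. A loss through this route would need a patient to fail 40 mg and then 20 mg daily, be stopped before completing 3 cycles, and be someone who would have completed them on every-other-day dosing. The documents give no frequency for that sequence. Section 12.5.2 does not mention rPFS, which section 12.1 names as primary, and the schedule in 6.1 continues imaging until progression.
- **That patients are put at risk of over-exposure.** The sentence errs toward stopping drug, so it creates no such hazard.

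**Conclusion.** The concern holds as an internal inconsistency: the 7.8.2 sentence is wrong as written. Its size is one dose level, with 1 reduction left where the plan permits 2. The number of patients affected is unknown; only those who fail both 40 mg daily and 20 mg daily could be. No statistical figure changes, and no effect on the primary endpoint is shown.

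The conclusion assumes that the synopsis, 7.8.1 and Table 7.2 with its NOTE express the intended ladder. Their agreement supports this, but only the sponsor can confirm it. No design decision is disputed, since either floor could be chosen if stated consistently. Severity is minor.

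**What to change.** Replace the 7.8.2 sentence with:

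*Subjects unable to tolerate 20 mg daily may be reduced to 20 mg every other day per Table 7.2, subject to Table 7.3 and the AE-specific discontinuation rules. Subjects unable to tolerate 20 mg every other day will discontinue study treatment.*

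The permissive verb in the first part keeps in force the Grade 4 rule in Table 7.3 and the events in 7.9.2 for which drug is stopped. The mandatory verb in the second part matches the Table 7.2 NOTE and 7.10. The synopsis, 7.8.1, Table 7.2 and 7.10 then need no change.

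If the sponsor instead intends 20 mg daily as the floor, the synopsis, 7.8.1 and Table 7.2 with its NOTE must be changed.

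The cost is one sentence in a protocol amendment: IRB approval before implementation (Statement of Compliance and 11.2.1), review by the drug supplier (11.2.1) and distribution to the sites. It has no statistical cost.
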